11.4.3 Analysis of secondary endpoints

In the analysis of secondary endpoints, continuous variables will be described

using mean \pm standard deviation or median (interquartile range); categorical variables will be described using counts (percentages). Missing values of the secondary endpoints will not be imputed, nor will sensitivity analyses be conducted for them.

11.4.4 Subgroup analysis

We will explore the differences in the primary endpoints between the two groups in different subgroups through subgroup analysis. The subgroups include gender (male; female), age (≤ 65 years old; > 65 years old), the relationship between the lower part of the tumor and the peritoneal reflection (above the peritoneal reflection; below the peritoneal reflection), as well as other variables that are independently related to the primary endpoint in the multivariate analysis. Logistic regression will be used for univariate and multivariate analyses, with effect sizes represented by OR and 95% CI, and subgroup interaction P-values will be calculated.

11.5 Exploratory Analysis

We will conduct an exploratory analysis of the situation of urinary tract infections. The main focus is to explore the independent related factors affecting urinary tract infections after rectal surgery. The analysis methods include univariate analysis, multivariate analysis, as well as subgroup analysis.

11.6 Interim analysis

This study does not include an interim analysis

11.7 Final analysis

We will conduct the primary endpoint analysis of the study after all patients have completed their first postoperative month follow-up and will publish the relevant research findings. The results of the exploratory analysis will be published separately as a post-hoc analysis

11.8 Data Monitoring Committee

This study establishes a Data and Safety Monitoring Board (DSMB), which is composed of senior surgeons, ethicists, and statistical analysts. The members of the DSMB are independent of this trial and have no competing interests that could influence the trial. The DSMB will receive and review the safety data of this trial. If the DSMB believes that the number of adverse events in the trial is biased between groups, they will notify the trial steering committee.

No interim analyses are planned in this study. However, after the study begins, the DSMB will assess the study results every six months and may meet earlier for assessments. The assessment content includes the recording of primary and secondary endpoints, adverse events, and the dropout rate of study samples. Except for the trial steering committee, DSMB members must not share confidential information with anyone outside the DSMB.

The interventional methods used in this study (intermittent catheter clamping and continuous catheter opening) are common clinical strategies for managing catheters after surgical procedures and do not impose additional risks on patients. Therefore, this study does not have predefined stopping criteria. However, if the regular assessments by the DSMB reveal that the urinary system-related safety indicators due to the intervention methods are significantly worse than the current domestic standards, the DSMB will submit its recommendations in writing to the trial steering committee. This may include requests to modify the trial plan, re-evaluate the quality of cases, or even suspend or terminate patient enrollment in the clinical trial.

12. Data collection and management

12.1 Case Report Form/Electronic Data Recording

The Case Report Form (CRF) includes the following primary outcome measures: incidence of urinary dysfunction, including bladder residual urine volume after the

first urination, rate of secondary catheterization, time from catheter removal to secondary catheterization (hours), method of secondary catheterization (suprapubic puncture/urethral catheterization), reasons for secondary catheterization, and urine volume drained after secondary catheterization (ml). Secondary outcome measures include: urinary tract infection status (white blood cell count in urine, bacterial content, and positive/negative urine culture before catheter removal), time to first urination after catheter removal (hours), bladder residual urine volume after the first urination (milliliters), CRBD grading assessment, bladder training quality self-assessment form for the bladder training group, postoperative complications within 30 days (incidence of complications, types of complications, and grading of complications), and urinary function assessment on the second day after catheter removal (ICIQ-SF, IPSS score). Other collected baseline indicators include: gender, age, underlying diseases and medical history (hypertension, diabetes, cardiovascular disease, cerebrovascular disease, history of pelvic surgery), history of benign prostatic hyperplasia in males (confirmed by medical history or imaging), preoperative IPSS score, preoperative ICIQ-SF score, preoperative radiotherapy and chemotherapy status, preoperative urine routine white blood cell count, preoperative urine routine bacterial count, preoperative urine culture results, ASA, BMI, preoperative imaging assessment results (preferably rectal MRI), including the distance from the lower edge of the tumor to the anal margin, the relationship between the lower edge of the tumor and the peritoneal reflection (above/below the peritoneal reflection), clinical T staging, clinical N staging, MRF status, EMVI status, surgery duration, surgical procedures, including low anterior resection (LAR), intersphincteric resection (ISR), abdominoperineal resection (APR), transanal TME (TaTME), Bacon surgery, stoma status (ileum/colon, single/double), surgical technique (robotic/laparoscopic), and postoperative pathological conditions (pathological T staging, pathological N staging, CRM, DRM). See the CRF form for details.

All patients who meet the inclusion criteria will be registered. For patients who are excluded due to the exclusion criteria, the specific reasons for exclusion need to be recorded. For the patients who eventually enter the randomization process, their

detailed information will be registered in the database. For patients who deviate from the randomized grouping for various reasons and those who deviate from the established intervention process during the intervention, the reasons for the deviation need to be recorded. All patients after randomization are required to record the relevant data completely in accordance with the content of the CRF.

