2.1 Objective

Primary Objective

This study investigated the effects of intermittent catheter clamping combined with active urination training (ICCAUT) on postoperative urinary dysfunction in patients after proctectomy.

Secondary Objective

To explore whether bladder training will increase the risk of postoperative urinary tract infections in patients after radical resection of rectal cancer.

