- 2) The patient requires secondary catheterization due to disease-related factors (such as secondary surgery, urethral injury, shock, altered consciousness, intestinal obstruction, hemorrhage, transfer to ICU, SOFA score ≥ 2 , etc.).

2.2.2 Secondary study endpoints and definitions.

Secondary endpoints of this study include: 1) Catheter-associated urinary tract infection status; 2) Time to first urination after catheter removal; 3) Grading assessment of catheter-related bladder discomfort (CRBD); 4) Post-catheter removal urinary function evaluation (using ICIQ-SF and IPSS scores); 5) Postoperative complications within 30 days (incidence of complications, types of complications, and grading of complications); 6) Incidence of residual urine volume greater than 200 milliliters after the first urination.

2.2.3 Other indicators and definitions.

Urinary tract infection is defined as an inflammatory response of the urinary epithelium to bacterial invasion. The diagnosis requires both of the following criteria to be met: 1) Urinalysis indicates a bacterial count above the normal upper limit, and 2) Positive urine culture. The time to first urination after catheter removal is defined as the time from the removal of the catheter to the patient's spontaneous urination, measured in hours. The time from the second catheterization to the removal of the urinary catheter is defined as the time interval from the first removal of the urinary catheter to the completion of catheter insertion by the nurse or suprapubic puncture by the ultrasound doctor after the clinician determines that the patient requires a second catheterization.

Complications within 30 days after surgery are assessed according to the Clavien-Dindo classification, and complications of grade II and above are recorded and analyzed. These include, but are not limited to, intraperitoneal bleeding,

gastrointestinal bleeding, anastomotic leak, chylous fistula, surgical site infection (intra-abdominal infection and incisional infection), intestinal obstruction, postoperative diarrhea, pulmonary infection, urinary tract infection, cardiovascular accident, cerebrovascular accident, and thrombotic diseases.

3. Study design.

3.1 Overall study design.

Single-center, prospective, two-arm, parallel-group randomized controlled study.

3.2 Study duration.

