3.2 Secondary

The secondary objective of this study is to investigate whether the ICCAUT strategy is associated with an increased risk of postoperative urinary tract infection.

4 Endpoints

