6.5.3 Analysis of secondary endpoints

In the analysis of secondary endpoints, continuous variables will be described using the mean \pm standard deviation or the median (interquartile range); categorical variables will be described using counts (percentages). Missing values for secondary endpoints will neither be imputed nor subjected to sensitivity analysis.

Secondary endpoints:

Variables	Type	Effect size	P value
Urinary tract infection	categorical variable: no, yes	Absolute risk difference (95% CI)	*.***
The time from catheter removal to the first micturition	continuous variable: hours	Difference (95% CI) by Hodges-Lehmann method	*.***
Catheter-related bladder discomfort (CRBD)	categorical variable: level 0, level 1, level 2, level 3	Absolute risk difference (95% CI)	*.***
ICIQ-SF score on the second day after the first removal of the urinary catheter	continuous variable: points	Difference (95% CI) by Hodges-Lehmann method	*.***

ICIQ-SF classification on the second day after the first removal of the urinary catheter	categorical variable: no or mild, moderate, severe	Absolute risk difference (95% CI)	*.***
IPSS score on the second day after the first removal of the urinary catheter	continuous variable: points	Difference (95% CI) by Hodges-Lehmann method	*.***
IPSS classification on the second day after the first removal of the urinary catheter	categorical variable: mild, moderate, severe	Absolute risk difference (95% CI)	*.***
Surgical Complications within 30 days after surgery	categorical variable: no, yes	Absolute risk difference (95% CI)	*.***
Specific types of complications	categorical variable: no, yes	-	-
.....	-	-
Clavien - Dindo Classification of Surgical Complications \geq III	categorical variable: no, yes	Absolute risk difference (95% CI)	*.***
Bladder residual urine volume $>$ 200 ml after the first voiding	categorical variable: no, yes	Absolute risk difference (95% CI)	*.***

Other outcomes of interest:

- Self-assessment form on the quality of bladder training, presented in the form of a bar chart.
- Postoperative hospital stays, continuous variable, measures in days;
- Duration of urinary catheter indwelling, categorical variable: within 1 day, 2 days, \geq 3 days;
- Time from catheter removal to second catheterization, categorical variable: within 1 day, 2 days, \geq 3 days;
- Volume of first urination after surgery, continuous variable, measures in milliliters;

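### The only secondary objective is postoperative UTI risk, but the sole planned UTI comparison reflects a pre-removal sample; UTIs recorded to day 30 get no planned effect estimate

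*Protocol*

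**What the plan says.** **Objective.** SAP 3.2 gives one secondary objective: "whether the ICCAUT strategy is associated with an increased risk of postoperative urinary tract infection". Protocol v2.0, section 2.1 has the same single objective.

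**Endpoint and definition.** Protocol v2.0, section 2.2.2 lists the first secondary endpoint as "1) Catheter-associated urinary tract infection status". Section 2.2.3 defines UTI by a raised bacterial count on urinalysis and a positive culture: "The diagnosis requires both of the following criteria to be met". No time window is given there, in SAP 4.2, or in the UTI row of the table in SAP 6.5.3.

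**Data collected.** Section 6.1.1 schedules a urinalysis and culture on admission, and section 6.1.2 schedules another before first catheter removal. No later culture is scheduled. Section 12.1 describes UTI status by urine white cells, bacterial content and "positive/negative urine culture before catheter removal".

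**Later infections.** Section 2.2.3 names UTI among the complications within 30 days of surgery, for which "complications of grade II and above are recorded and analyzed". These belong to a different secondary endpoint, the fifth.

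**Analysis.** In the SAP 6.5.3 table, the UTI row has an absolute risk difference, 95% CI and P value. The row for specific complication types has a dash for both effect size and P value.

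**The concern.** The objective is worded for the postoperative period, while the one UTI row with a planned comparison is fed by a sample taken before the catheter first comes out. Residual urine after the first void and re-catheterisation within 7 days, which make up the primary endpoint, both come after that sample. The trial expects this composite to differ by arm (44.7% against 59.3%, protocol 11.1). Any effect on infection that follows from it, in either direction, would not show in the UTI row as collected.

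The background section notes that training may raise UTI rates, so this is the trial's main question about harm. If the pre-removal row shows no difference, it could be read as no increase in postoperative UTI, although it observes only the time up to removal. The 30-day data that bear on the rest are on the CRF but have no planned estimate.

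**Working it through.** **1. When the sample is taken.** Protocol section 10 sets the start of training at 9:00 am on postoperative day 1 and removal at 9:00 am the next day. The interval is 24 hours, and the sample precedes removal. The interval lengthens if removal is postponed, which section 5 allows. From day 2 to day 30 there are 30 − 2 = 28 further days with no scheduled culture.

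**2. Which UTIs reach the UTI row.** Three places point the same way:
- Section 6.1.2 schedules a single post-randomisation urinalysis and culture.
- Section 12.1 ties UTI status to pre-removal results.
- Section 12.2 requires endpoint data within two days of catheter removal and gives 30-day complications a separate entry deadline.

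Against this, the definition in section 2.2.3 and the SAP row state no window. The pre-removal reading is therefore an inference from three consistent passages.

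**3. How each source is analysed.**

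| Source | Period | Criterion | Planned comparison (SAP 6.5.3) |
|---|---|---|---|
| Pre-removal sample | To first removal | Urinalysis and culture | Risk difference, 95% CI, P |
| UTI as a complication | To day 30 after surgery | Clavien-Dindo grade II or above | None (dashes) |

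**4. Size.** The documents give no UTI rate and no power for UTI. The stated sample size concerns the primary endpoint only, and it reproduces: with unpooled variance and two-sided 0.05, n = (1.960 + 0.842)² × (0.447 × 0.553 + 0.593 × 0.407) / 0.146² = 179.9, i.e. 180 per group, and 180 / 0.9 = 200.

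For scale only, take *assumed* control UTI rates with 200 per arm, two-sided 0.05, and the normal approximation with pooled variance under the null. The power to detect a doubling is:
- 2% to 4%: 21.5%
- 5% to 10%: 47.5%
- 10% to 20%: 80.2%

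Unless UTI is fairly common, a non-significant P value on either row says little about absence of harm. The confidence interval should carry the conclusion.

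**The case against.** The endpoint is named as catheter-associated infection, so sampling at the end of catheterisation is coherent, and the whole clamping period falls inside the interval it covers. That stands: the pre-removal row is legitimate and should stay.

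Later UTIs are not lost. They are to be reported by type among the 30-day complications, and the monitoring board reviews adverse events for imbalance. SAP 6.1 also says, as a general rule, that risk differences and intervals will be calculated for categorical variables. This stands in part. The dashes in the 6.5.3 table depart from that general rule for exactly these rows, and board review is not a reported comparison.

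Three stronger readings are tempting, and the documents do not support them:
- *Later UTIs are excluded by rule.* No passage says so. Section 12.1 is a list of fields that refers on to a CRF form not reproduced in these documents.
- *The short window measures the share of infections missed.* It is a share of calendar time. Equating the two would need a constant infection rate to day 30, which nothing in the documents supports.
- *One merged 30-day row should carry the conclusion.* That row would mix a laboratory result with clinical events of grade II or above. It would rely partly on reports after unblinding at discharge (section 5.2), some by phone or questionnaire (section 6.2). Fewer infections after re-catheterisation in the training arm could also offset early harm from clamping and hide it.

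**Conclusion.** The concern holds in a limited form. As scheduled and collected, the UTI endpoint reflects one sample about 24 hours after training starts when removal is on time. UTIs recorded to day 30 have no planned effect estimate. The only secondary objective, as worded, is therefore only partly addressed by the planned comparisons. The primary analysis is unaffected.

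This rests on reading the UTI row as pre-removal, which is the natural reading but is not stated, and on the table's dashes overriding the SAP's general rule. If the sponsor intended otherwise, the SAP should say so. The effect on the result cannot be quantified, because neither the UTI rate nor the share arising after removal is given.

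**What to change.** In SAP 6.5.3:
- Label the existing row *UTI on pre-removal sample*.
- Add a separate row, *UTI recorded as a complication within 30 days (grade II or above)*, with absolute risk difference and 95% CI.
- Treat any combined row as supportive only, with its components shown. The rows can overlap because the 30 days run from surgery, so give the number of patients counted in both.
- Draw the conclusion on the secondary objective from both rows, and state that no difference on the pre-removal sample does not by itself show no increase in postoperative UTI.

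Use the same label where UTI appears as a candidate predictor (6.5.1) and in the exploratory analysis (6.6).

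The cost is SAP wording and one table row from data already on the CRF, with no new sample or visit. The SAP was written with 362 of 400 patients enrolled. If analysis has not begun, the row can still be added as pre-specified; otherwise it should be marked as added later.

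Limits to state beside the new row: 30-day UTIs may lack culture confirmation, count only at grade II or above, may be reported after unblinding at discharge, and may partly reflect differences in re-catheterisation.

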12.2 Data management

Data collection will be conducted by the CRC, who will verify and collect information on patient enrollment, withdrawal, achievement of primary endpoints, and measurement of secondary endpoints daily. Two graduate students will serve as data entry personnel. The two graduate students and the CRC will jointly collect baseline data. Data entry will be performed using a dual-entry method, with one person entering the data and another verifying it. Both paper and electronic versions of the CRF will be entered simultaneously. Baseline data will be entered on the day of surgery, information related to primary and secondary endpoints will be entered within two days of catheter removal, and pathological and other hospitalization information must be entered within one week after patient discharge. Complications within 30 days after surgery must be entered within 30 days after surgery. To protect patient privacy, all patients will be coded and identified using random numbers. These random numbers do not include patient initials or date of birth. Investigators will have a decoding list that specifies the random numbers of patients in their site's files and their patient identification numbers.

13. Ethics and Morality

13.1 Ethics committee

Before the study begins, this trial will obtain ethical approval from the ethics committee of our hospital.

13.2 Patient information and informed consent

Eligible patients should receive personal notification from the treating surgeon and be provided with written information related to the trial. Before entering the randomization of the study, each patient must provide informed consent in accordance with the guidelines of the ethics committee. Patients will have at least 24 hours to decide whether to participate in the study and can withdraw from the study at any time without reason.

The informed consent process should be conducted by a physician of the attending level or higher within our group. The information provided to patients during informed consent includes:1) A statement that the trial involves research;2) A full and fair explanation of the procedures to be followed;3) A full explanation of the nature, expected duration, and purpose of the research;4) A description of any risks or discomforts that the patient can reasonably expect;5) A description of any benefits that can be reasonably expected;6) A statement that patient data will be handled with care and confidentiality, and the duration of data retention (15 years);7) A statement that patient biological materials will be retained for 15 years;8) A statement about voluntary participation and withdrawal, indicating that refusal to participate in the trial involves no penalty or loss of benefits to which the patient is otherwise entitled, and that the patient may stop participating at any time without penalty or loss of benefits, in which case the patient will receive standard care of the same quality.

14. Definition of study completion

The study is considered complete when all enrolled patients have completed a one-month follow-up.

15. Trial organizational structure

This study is conducted at a single medical center—The First Hospital of Jilin

University. The trial steering committee members include [name] , [name], [name], [name] , and [name] . The Data and Safety Monitoring Board (DSMB) is composed of senior surgeons, ethicists, and statistical analysts. Each member of the DSMB is independent of this trial and has no competing interests that could influence the trial. This clinical trial is funded by the General Surgery Center Discipline Special Zone Project of The First Hospital of Jilin University, with the project number: 04050520005.

We did not involve patients or the public in the design of this study or in the oversight of its implementation. We also have no plans to share the data from this study with the patients who participated in the enrollment.

16. Confidentiality and data security

During the study, only data entry personnel and the DSMB are aware of the data situation, and others cannot access the database to know specific patient data. DSMB members can be aware of patient allocation and trial-related data. The DSMB will discuss the relevant results of the data with the trial steering committee members. Except for the trial steering committee, DSMB members must not share confidential information with anyone outside the DSMB.

For decisions and recommendations formed through discussions by the DSMB, the DSMB will submit these recommendations in writing to the trial steering committee. Additionally, the CRC will also receive these recommendations to be discussed at the trial steering committee meeting. The content of the meeting needs to be stored and secured by the DSMB members after the meeting, so that it can be reviewed in comparison with the next report.

17. Insurance and compensation.

All enrolled patients have purchased medical commercial insurance in

collaboration with our hospital and an insurance company before surgery. The insurance will compensate for surgery-related complications and surgery-related deaths. For each patient enrolled in the trial, an enrollment compensation of 100 yuan will be provided to enhance the patient's compliance.

18. Publication statement

The data will not be published before the collection of primary outcomes is completed. We will conduct the primary endpoint analysis of the study after all patients have completed their first postoperative month follow-up and will publish the relevant research findings. The order of authors will be arranged from highest to lowest based on the number of enrolled cases. The results of the exploratory analysis will be published separately as a post-hoc analysis after the publication of the results of the primary endpoint.

19. References

1. Williamson ML. Reducing post-catheterization bladder dysfunction by reconditioning. *Nurs Res.* 1982;31(1):28–30.
